apparatus calibration. Each trial begins after subjects fixate for 500 ms on a central fixation spot. After a brief (300-600 ms) delay, either a training stimulus (3 f.c. bright light from LED + 75 dB broadband sound from speaker) is activated at 45° of eccentricity in the blind field, or (with lower frequency) a single visual stimulus with same parameters is activated at 45° in the intact or blinded field, or no stimulus is presented at all. Subjects are requested to saccade to any stimuli that appear and otherwise maintain fixation. Stimuli remain active for 3 seconds or for 500 ms after a saccade is made, whichever is shorter. Multisensory training the VR apparatus uses an identical procedure, with the visual and auditory stimuli being an equivalent stimuli produced at the same virtual distance and positions. Trials are presented at a rate of 1/5 sec and continue for 60 mins. Depending on whether it is a purely training or training/testing session, this allows for 500 – 1000 presentations of the visual-auditory training stimulus per session along with 200-400 trials containing single visual or no stimuli. This greatly exceeds the number required in the animal model, and provides the best opportunity for success in sessions of practical duration.

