Visual tests: Tests of vision will be conducted on both sides of space and are organized in trials. In each trial the subject acquires fixation for 500 ms before a stimulus is presented after a randomized delay (200-600 ms). Subjects are required to saccade or point to (i.e., “indicate”) the stimulus or stimulus-target (<10° error) within 2 seconds or their response is scored as a “No-Go”. They are informed of whether their response was “correct” or “incorrect” via an auditory tone after a confidence report (see below). Each test has one or more stimulus levels that are manipulated to create the independent variable(s) of psychometric functions of performance. Detection/Localization: Trials contain either a visual target (LED or 5X5° white square) of manipulated contrast at a randomly-selected location outside of central space (correct response: indicate), or no stimulus anywhere (correct response: No-Go). Competition: Trials contain either no stimuli (correct response: No-Go), or 1 stimulus at a randomly-selected location on either side of space (correct response: indicate), or 2 identical visual stimuli at homotopic locations with randomized eccentricity (correct response: indicate both). Stimulus contrast is manipulated. Multisensory Integration: Trials contain either no stimuli (correct response: No-Go) or brief (100 ms) low-contrast visual or low-volume auditory stimuli presented alone or together at a randomly-selected location (correct response: “indicate”). This evaluates whether the senses can be used synergistically in contralesional space to enhance localization as in intact subjects. Frequency Discrimination: Pairs of oriented gratings with manipulated Δ° and Δf presented on either side of space (correct response: indicate if same, No-Go if different). Shape Discrimination: Unilaterally-presented pairs of simple Efron shapes (see (Whitwell et al., 2014)) with manipulated similarity (correct response: indicate if same, No-Go if different). These shapes consist of stacked rectangles or smoothed splines whose similarity can be quantitatively manipulated and provide a robust, common, and controlled way of assessing shape perception in normal and compromised populations. Subjects will also have the opportunity to report qualitative aspects of any changes in their visual perception during the study.

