Testing conditions: Each of the above tests will be evaluated under two different ambient light conditions: normal indoor levels (~300 lux) and darkness (~.001 lux). Lighting conditions are set during the “briefing” period and changed during the “break” (see below), which gives time for dark- or light-accommodation. We will also evaluate conditions in which stimuli are either stationary or moving.

Confidence reports: Subject performance is tracked online and summarized in a numeric “game score” displayed to them after each testing run (see below). On each trial, after making their response (either indicating or No-Go), subjects verbally report a confidence score of 1-3 indicating their confidence in whether they are guessing (1), are unsure (2), or are very confident (3) in their response. The confidence rating translates to the points wagered for that trial. Correct responses increase the game score by double the wagered amount, while incorrect responses decrease the score by the wagered amount.

Testing structure: A 2 hr testing session is divided into two 45-min sets separated by a 10 min “break”, with a 10 min “briefing” period at the beginning and 10 min “recapitulation” period at the end.

Training/testing sessions contain only a single set. Each trial requires <3-5 seconds. Trials of a single task, stimulus level, and testing condition are conceptually organized into “runs” of 10-12 trials (~.75-1 min/run with warmup/cooldown). Two runs with the same task and testing condition, but 1-4 stimulus levels, are intermixed within a “block” of 20-96 trials (2-8 min/block). This structure provides ample time to test two blocks of each visual test (e.g., one block stationary, the other moving) within each set. However, testing will be customized for each subject in this pilot to focus on performance limits; e.g., by reducing testing of basic capabilities in later sessions, not extensively testing multiple levels of higher-order capabilities when lower-level ones are not yet intact, and initially testing with wider ranges of stimulus levels before proceeding to narrower ranges.

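### Read literally, the No-Go rule scores a response on a no-stimulus trial as correct, and a late or misplaced indication on a 'different' trial too; no section states otherwise

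*Combined protocol and SAP*

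**What the plan says.** All references are to the combined protocol and SAP.

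- **General rule (Visual tests).** It stands before the five tests. A participant must indicate the stimulus or its target with "<10° error) within 2 seconds or their response is scored as a “No-Go". Here No-Go is a default score that can be given to a response actually made.
- **No-stimulus trials (Visual tests).** Detection/Localization includes trials with a target "or no stimulus anywhere (correct response: No-Go"). Competition says: "Trials contain either no stimuli (correct response: No-Go), or 1 stimulus at a randomly-selected location on either side of space". Multisensory Integration also has empty trials with No-Go as the correct answer.
- **'Different' trials (Visual tests).** For both Frequency and Shape Discrimination: "correct response: indicate if same, No-Go if different".
- **No-Go as a choice (Confidence reports).** "after making their response (either indicating or No-Go), subjects verbally report a confidence score of 1-3". Here No-Go is what the participant does instead of indicating.
- **Game score (Confidence reports).** "Correct responses increase the game score by double the wagered amount, while incorrect responses decrease the score by the wagered amount". The wager is the confidence score, 1 to 3.
- **Analysis (Analytical Plan).** The tests yield curves of percent correct against stimulus level. No false-alarm rate or bias-corrected index is named.

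**The concern.** No-Go carries two meanings: the participant's decision not to indicate, and the label for any response that is late or lands 10° or more from a target. Where No-Go is the correct answer, the second meaning turns an error into a correct response.

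No-stimulus trials are an important guard against mistaking guessing for seeing. If their accuracy is 100% by rule, they cannot show that a participant has started to respond more freely. That matters here because the Design is a single group of 6 without a control arm, and the Outcome Measure(s) section counts recovery of any visual function as a success. More frequent guessing into the blind field would raise hits by chance, with no recorded cost.

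The same scoring drives the correct/incorrect tone and the game score. A rule that pays for false alarms could teach participants to guess, and behaviour shaped in that way cannot be undone by rescoring.

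**Working it through.** The plan gives no false-alarm figure to reproduce, so the check is mainly one of logic.

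**1. The rule applied to each trial type**

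| Trial | Correct answer | What the participant does | Score under the literal rule |
|---|---|---|---|
| No stimulus | No-Go | Any saccade or point | No-Go, correct |
| 'Different' pair | No-Go | Late or off-target indication | No-Go, correct |
| 'Different' pair | No-Go | On-target indication in time | Indication, incorrect |
| Target present | Indicate | Late or off-target indication | No-Go, incorrect |
| Target present | Indicate | Withholds | No-Go, incorrect |

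The first two rows are the problem. The last two are pooled, which loses detail but does not alter accuracy.

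**2. Accuracy on no-stimulus trials**

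Let f be the true false-alarm rate (assumed; not in the documents). Literal accuracy is 100% for every f. If false alarms are errors, accuracy is 1 − f: 90%, 75%, 50% and 0% for f = 10%, 25%, 50% and 100%. At f = 25%, 12 empty trials would hide 12 × 0.25 = 3 errors.

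**3. Game score for one false alarm with wager w (1 to 3)**

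Scored correct: +2w, so +2 to +6. Scored incorrect: −w, so −1 to −3. The difference is 3w, or 3 to 9 points.

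**4. Illustration: a participant with no vision who guesses on every trial**

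Neither the share of empty trials, c, nor the spread of guesses is in the documents. Pooling empty and target trials into one score is also an assumption. With chance hit rate h, the literal score is c + (1 − c)h, the score with false alarms as errors is (1 − c)h, and a participant who always withholds scores c.

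- *Targets and guesses uniform over 10–90° of the blind side:* h = 1 − (1 − 10/80)² = 0.234. With c = 0.5, the literal score is 0.5 + 0.5 × 0.234 = 62%, against 0.5 × 0.234 = 12%. Always withholding scores 50%. Other spans give h = 0.22 (5–90°), 0.27 (20–90°) and 0.36 (10–60°).
- *Guesses uniform over the 180° arc:* h = 20/180 = 0.111, ignoring the ends of the arc.

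| c | Literal rule | False alarms as errors | Always withholds |
|---|---|---|---|
| 20% | 28.9% | 8.9% | 20% |
| 33% | 40.7% | 7.4% | 33% |
| 50% | 55.6% | 5.6% | 50% |

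The levels depend on the inputs; the direction does not. Under the literal rule, constant guessing scores higher than withholding. With false alarms as errors, it scores lower in every case shown.

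**The case against.** The strongest reply is that the rule was never meant for empty trials. It follows a sentence about a trial in which a stimulus appears ("In each trial the subject acquires fixation for 500 ms before a stimulus is presented after a randomized delay (200-600 ms") and it speaks of indicating a stimulus. The Confidence reports section treats indicating and No-Go as alternatives, and the Interventions and Interactions section calls no-stimulus trials catch trials, which makes accuracy of 100% by rule an unlikely intent. This stands as to intent. A reader might infer that the plan instructs staff to count false alarms as correct; the documents do not say so. It is the literal consequence of a rule placed ahead of tests that contain empty trials. On the kinder reading, those trials have no explicit rule for a response that is made.

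A reader might also see a direct conflict with the Multisensory training section ("Subjects are requested to saccade to any stimuli that appear and otherwise maintain fixation"). That text describes training and does not use the term No-Go. It supports the withheld-response meaning but does not define it.

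Three further points stand:

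- The 62% and 12% figures pool empty and target trials, whereas the Analytical Plan describes curves by stimulus level and by location or side. An empty trial has none of these, and its rescoring leaves target-trial accuracy unchanged. This does not help the discrimination tests, where a 'different' pair does have a stimulus level.
- Catch trials are not the only safeguard. The 10° localization limit, manipulated contrast, confidence reports, the pre-training baseline, comparison between sides, and separate Humphrey and kinetic fields also help.
- Latency and final eye position are recorded, and hand position in the VR apparatus, so analysis scores can be recovered. The feedback that participants received cannot.

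**Conclusion.** The concern holds as a scoring ambiguity with a wrong literal result. As written, the rule makes any response on a no-stimulus trial correct in Detection/Localization, Competition and Multisensory Integration, and makes late or off-target indications correct on 'different' trials in the two discrimination tests. The intended scoring is probably the conventional one, but no section states it.

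The size that follows from the text alone is accuracy fixed at 100% on empty trials whatever the true false-alarm rate, and a swing of 3 to 9 game points per false alarm. The pooled percentages are illustrations under assumed inputs, not estimates of bias in this trial. The documents do not show that false alarms have been or will be scored as correct, nor that a guessing participant would necessarily pass as recovered. They do leave open a route by which a shift towards guessing could be read as recovery, in an uncontrolled study of 6 that names no false-alarm rate. That is enough to warrant correction before scoring begins.

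**What to change.** In the Visual tests section:

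1. Restrict the 10° and 2-second rule to trials on which indicating is the correct response.
2. State that any indication on a no-stimulus or 'different' trial is a false alarm and is incorrect, in the analysis and equally in the feedback tone and the game score.
3. Define No-Go as a withheld response, and record withheld, late, off-target and on-target responses as separate outcomes.

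In the Analytical Plan, report hit rates alongside false-alarm rates by subject, session and condition.

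The cost is wording, a check that the scoring software follows it, and a recode from latencies and end positions already recorded. Some accuracy figures may become less favourable. If sessions have already run with feedback under the literal rule, report this, because rescoring cannot remove its effect on later responding and confidence.

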Outcome Measure(s). A variety of dependent measures are extracted during these experiments, including responses selected, response delay/timing, response accuracy, etc. Responses to visual stimuli will be evaluated over the duration of the experiment to assess recovery of function. The main hypotheses state that subjects will either be able to perform some task at some level or not at all, although there is likely to be quantitative variation in parameters such as response latency, threshold sensitivity, and confidence. In this context, recovery of any visual function is a success. Below we outline two sets of predictions identifying the most credible outcomes and elaborate on the significance of each, although mixed results are also possible.

Modest Rehabilitation: It is possible that hemianopic patients will recover basic reflexive visual functionality, but their capabilities will be limited to those typically associated with “blindsight”. In this case, they would be able to detect and localize visual stimuli in the rehabilitated field and use auditory information to enhance this capability. However, they would always choose the intact field in competition tasks, be unable to perform any higher-order discriminations in the contralesional field, and would always

have low confidence in that field even when they can perform visually – a result falling short of that seen in the animal model. Such a result will be less than expected but is not without clinical value: by acquiring the ability to respond to contralesional visual stimuli, rehabilitated subjects can bring them into the sighted field for further analysis.

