The Expected Result: However, our expectation is that hemianopic patients will recover visual functionality similar to that observed in the animal model, although the timing of the recovery and the quantitative parameters of the functional endpoints may differ. This means that, after a few weeks of training, they will be able to perform each of the tasks at some level under some conditions. We expect performance to be best under scotopic conditions and for moving stimuli; i.e., testing conditions best suited to driving robust visual responses in SC-mediated visual pathways. There is likely to be an initial separation between performance in visual tasks and confidence, with the former recovering faster than the latter, as the brain adapts and reinterprets activity patterns in remaining circuits as definitive of the visual stimuli generating them.

In either case, future directions will examine the means to improve the rehabilitation method (including calibrating subjects to the sensation of contralesional visual stimuli), examining the impact of the strategy on other domains impacting quality of life (e.g., navigation), an analysis of the underlying circuits using magnetoencephalography, evaluation of the sensitivity of different individual features to the procedure (e.g., age, gender, delay from lesion onset to treatment), a deeper exploration of the limits of functional recovery, and the formalization of a clinical trials protocol.

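### Correct/incorrect feedback on every blind-field test trial means that a rise in confidence does not by itself separate recovered vision from blindsight

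*Combined protocol and SAP*

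**What the plan says.** All references are to the combined protocol and SAP.

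- **Methods and Measures, Visual tests.** "Tests of vision will be conducted on both sides of space and are organized in trials", so the blind field is included. On feedback, participants learn whether each response was right or wrong "via an auditory tone after a confidence report (see below"). No exception is given by field, task, baseline or re-assessment.
- **Methods and Measures, Confidence reports.** Performance is also "summarized in a numeric “game score” displayed to them after each testing run". The rating concerns the response and is not a rating of seeing: "subjects verbally report a confidence score of 1-3 indicating their confidence in whether they are guessing (1), are unsure (2), or are very confident (3"). The rating is the stake for that trial: a correct response gains twice the stake and an incorrect one loses the stake.
- **Outcome Measure(s), Modest Rehabilitation.** This result has three marks: intact-field choice in competition, failure of higher-order discrimination, and that participants would always "have low confidence in that field even when they can perform visually".
- **Outcome Measure(s), The Expected Result.** Performance and confidence are expected to separate at first, "with the former recovering faster than the latter, as the brain adapts and reinterprets activity patterns".
- **Analytical Plan.** Confidence scores enter a multilevel regression on time, subject and side of space. No feedback term and no trial-level analysis of confidence against accuracy is named.

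**The concern.** Confidence is meant to show whether a participant who can respond on the blind side also sees there. The rating asks how sure the participant is of being right, and the test then tells them whether they were. Giving the report before the tone protects only the current trial. Later trials, blocks and weekly sessions are all informed by earlier tones.

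A person with accurate but unaware responding could therefore move from guessing to very confident through knowledge of results alone. That gives performance first and confidence later, which is the order the plan reads as the brain reinterpreting its activity. At stake is the meaning of the confidence outcome in a study intended to support larger trials.

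There is a second, smaller consequence. The training procedure mentions no tone and the tests do, so each re-assessment is also reinforced practice for the blind field.

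**Working it through.** **1. Tones per block (plan's own figure).** Testing structure gives two runs of 10 to 12 trials at 1 to 4 stimulus levels. 2 × 10 × 1 = 20 and 2 × 12 × 4 = 96. This reproduces the stated 20 to 96 trials per block, with one tone per trial.

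**2. Blind-field tones per set.** A block can mix intact-field, blind-field and no-stimulus trials, and the plan gives no split. I assume one third are blind-field. In the Modest scenario the successes come mainly from detection and localization, so I count only that test, at two blocks per set:
- shortest blocks: 2 × 20 = 40 trials, and 40/3 ≈ 13 blind-field tones;
- longest blocks: 2 × 96 = 192 trials, and 192/3 = 64 blind-field tones.

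**3. What the wager rewards.** With stake w and believed accuracy p, the expected score is w × 2p − w × (1 − p) = w(3p − 1). This is positive once p exceeds 1/3, and the top rating then pays best. At p = 0.5 the expected score is 0.5, 1.0 and 1.5 for ratings 1, 2 and 3.

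**4. How quickly tones reveal this.** If true blind-field accuracy is 0.6 (assumed), the observed hit rate exceeds 1/3 with binomial probability 0.945 after 10 blind-field tones and 0.994 after 20.

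**5. Illustration of an unaware learner.** All inputs are assumptions. The prior belief in own accuracy is 0.20, weighted as 20 trials. The rating is 1 if belief is below 1/3, 2 up to 1/2, and 3 above. The participant has no knowledge of which individual trials are right. Expected belief after n blind-field tones is (4 + pn)/(20 + n). At p = 0.6 it passes 1/3 at n = 10 and 1/2 at n = 60; at p = 0.8 it passes 1/2 at n = 20. Simulated mean ratings, with a little noise in the belief, were:

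| True accuracy | No tone | Tone, first 10 | Tone, trials 40–50 | Tone, last 50 of 400 |
|---|---|---|---|---|
| 0.6 | 1.0 | 1.20 | 2.35 | 2.93 |
| 0.7 | 1.0 | 1.29 | 2.75 | 3.00 |
| 0.8 | 1.0 | 1.38 | 2.96 | 3.00 |

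The area under the curve for confidence separating correct from incorrect trials was 0.50 throughout, with or without the tone. Average confidence rises, but confidence does not track correctness.

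**6. Resulting lag.** At 64 blind-field tones per set, 40 to 50 tones fall within one set. At 13 per set they take 40/13 ≈ 3.1 to 50/13 ≈ 3.8 sets. Training/testing sessions hold one set and testing-only sessions two, so four sets span about three alternating weekly sessions. Feedback learning could therefore produce a lag of anything from under one session to about three weeks.

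**The case against.** The other side has real force on several points.

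- **Other criteria remain.** The Expected result requires some performance on every task, and the Modest result is also defined by competition choice and failed discrimination. Raised confidence alone cannot turn one into the other. This stands. Two limits apply: the tone follows those trials too, and Testing structure restricts higher-order testing while lower-level abilities are not intact.
- **Low confidence is still informative.** If it stays low despite feedback, it points to blindsight. This stands; the ambiguity runs one way.
- **A long lag would count against feedback learning.** True if learning is fast. But the plan gives no duration for the initial separation and the learning rate is unknown, so the planned analysis could not use the lag to decide.
- **First recovery comes earlier.** The Design paragraph has it sought in training-session probes, with repeated re-assessment only afterwards. The Humphrey and kinetic fields are separate clinical tests with no tone described. This stands and limits the practice argument to later battery gains.
- **Seeing is also reported directly.** Qualitative reports and diaries are collected, but informally, and neither enters the Analytical Plan.
- **Confidence does not decide success.** In this six-person pilot, recovery of any visual function counts. This stands, so the point concerns interpretation of one outcome and not the study's success criterion.

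A reader might also infer that one 20-trial block is enough to learn from. With 85% accuracy assumed, 17 of 20 gives an exact 95% interval of about 0.62 to 0.97, but that treats every tone as blind-field. If a third are, 6 of 7 gives about 0.42 to 0.996, which includes 50%. If half are, 8 of 10 gives 0.44 to 0.97 and 9 of 10 gives 0.55 to 0.997. The documents do not support the one-block claim.

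**Conclusion.** The concern holds in a limited form. As the plan is written, a rise in blind-field confidence does not by itself distinguish recovered vision from blindsight, because trial-by-trial feedback and the game score can produce it without awareness. Under the assumed inputs the possible shift covers most of the 1 to 3 scale: from 1.0 to about 2.4 to 3.0 after 40 to 50 blind-field tones. Accuracy, prior belief, rating thresholds and the blind-field share of trials are all assumptions; the documents give none of them. The direction of the effect needs only that participants use the feedback they receive.

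Two stronger readings are tempting and are not supported. One is that confidence can no longer separate the two outcomes at all, or that a blindsight-only participant could pass as the Expected result; the other marks and persistently low confidence argue against it. The other is that improvement cannot be credited to multisensory training. Feedback adds an avoidable rival explanation for gains across the repeated re-assessments. It does not do so for first recovery in the training probes or for the Humphrey and kinetic fields. The attribution limit that comes from having a single group would remain with the tone off.

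**What to change.** 1. At baseline and at re-assessments, run test blocks with the tone off and the game score withheld until the session ends. Because learning carries over, blind-field trials should be free of feedback throughout these assessments; the tone can stay for intact-field warm-up and practice.
2. State in Outcome Measure(s) that the confidence part of the Modest-versus-Expected distinction is judged on those blocks only.
3. Add to the Analytical Plan a pre-specified trial-level analysis of whether blind-field confidence separates correct from incorrect trials, within stimulus level and testing condition. It uses data already collected. An area near 0.50 alongside rising mean confidence would suggest learning from feedback.

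The cost is a software setting and protocol wording, with no added visits or participants. The downside is slightly less engaging testing and a delayed wager payoff.
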